# 4.9.3 Offsite Testing

In a separate subset of 21 patients (7 per location), LFR-260 testing will be completed by the ECP operators offsite at each location.

After the initial LFR-260 and traditional phoropter is complete within the clinic, participants in the offsite testing cohort will be taken to a non-clinical setting for the following procedure:

- 1. An additional LFR-260 will be set up in a remote location (room separate from clinic).
- 2. The patient will be taken to the remote room, and the ECP will perform the refraction.
- 3. Best Corrected Visual Acuity will be measured and collected.
  - a. Results will be captured to compare against the initial LFR-260 refraction results.

# 4.9.4 Remote Testing

In a separate subset of 21 patients (7 per location), LFR-260 testing will be completed by the ECP operators remotely at each location.

After the initial LFR-260 and traditional phoropter is complete, participants in the remote testing cohort will remain in the clinical setting for the following procedure, while the ECP relocates to an area outside of the exam room:

- 1. The patient will be shown the LFR-260 and site staff will oversee the telehealth refraction remotely on the LFR-260 by the ECP.
- 2. Results for the Best Corrected Visual Acuity will be collected.
  - a. Results will be captured to compare against the initial LFR-260 refraction results.

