# Statistical Considerations

The objective of the statistical analysis is to evaluate agreement in sphere, cylinder, and axis measurements between LFR-260 and traditional refraction performed by a traditional phoropter. Specifically, the subjective manifest refraction measured by means of a traditional phoropter will serve as the reference control and is considered to be the gold standard for the purpose of this evaluation.

The accuracy of the acuity measurement obtained by the LFR-260 will be evaluated for both cases (uncorrected, corrected) measured with the conventional phoropter. It will be assessed comparing the LFR-260 acuity measurement to the conventional acuity measurement using a Snellen chart (scored to the letter), with similar analyses used for the refractive components.

For each measurement, the paired difference will be computed. Good clinical agreement is defined a priori as  $\leq \pm 0.5$  D for sphere and cylinder measurements and  $\leq \pm 10$  degrees for axis measurements for subjects with low astigmatism and  $\leq \pm 5$  degrees for axis measurements for subjects with low astigmatism.

The unit of analysis will be the individual eye. Overall device performance will be summarized as the number of and percentage of eyes meeting three of the good clinical agreement criteria listed above.

the mean of measurements will characterized.

A supporting analysis will evaluate the vector difference between investigational device measurements and the gold standard in terms of sphere and cylinder measurements. The vector differences is square root of (X1-Y1) + (X2-Y2) where the X1 and X2 are measurements of sphere and cylinder using the investigational devices and Y1 and Y2 are the same measurements using the gold standard.

Homogeneity of treatment effects across sites will be evaluated comparing site level differences between the investigational device and the gold standard separately for sphere, cylinder, and axis and also for the vector analysis of sphere and cylinder.

Similarly, differences between measurements from the investigational device and the gold standard device will be summarized by gender, age category, race, and ethnicity to investigate consistency or heterogeneity of the treatment effect across those subgroups, separately for sphere, cylinder, and axis and also for the vector analysis of sphere and cylinder.

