# 1.2 Device Name and Intended Use

The LFR-260 is intended to be used for distance vision testing in any environment, may it be in optometric clinics or in the field outside of the clinic, because of its compact form factor and portability.

The LFR-260 is an application-controlled instrument providing capabilities for distance vision testing including sphere, cylinder, and axis. The visual acuity and eye subjective manifest refraction determination will always be administered by an eye care professional (ECP) licensed and registered by the appropriated body in the region intended to be used. The instrument is designed in a way that it will only work with approved personnel and the use of secure credentials.

The device is intended to be used in patients aged from 12-65 years old with healthy visual systems and a refractive error no bigger than (+10 to -15D) and astigmatism no bigger than 2.5D (if any).

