# 4.10 Study Duration

All subjects will be followed only for the initial visit as no follow-up assessments are expected after the initial visual acuity testing is complete.

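### Offsite and remote LFR-260 refractions are compared only with the initial LFR-260 reading, so their agreement with the phoropter, the declared gold standard, is never estimated

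*Combined protocol and SAP*

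**What the plan says.** The synopsis (Statistical Considerations) fixes the reference: "the subjective manifest refraction measured by means of a traditional phoropter will serve as the reference control". Sections 2.5.1 and 7.4 define good clinical agreement only against that reference: sphere and cylinder within 0.5 D, plus an axis limit that depends on the degree of astigmatism.

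The claimed use is wider than the clinic. Section 1.2 states: "The LFR-260 is intended to be used for distance vision testing in any environment". Section 4.2 adds fully remote refraction.

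Two subsets address those uses. Section 4.9.3 reads: "In a separate subset of 21 patients (7 per location), LFR-260 testing will be completed by the ECP operators offsite at each location". Section 4.9.4 describes a remote subset of the same size. Both sections say of the added refraction: "Results will be captured to compare against the initial LFR-260 refraction results". In both, the phoropter reading already exists. For offsite testing: "After the initial LFR-260 and traditional phoropter is complete within the clinic". For remote testing: "After the initial LFR-260 and traditional phoropter is complete, participants in the remote testing cohort will remain in the clinical setting". Section 4.10 confirms one visit: "All subjects will be followed only for the initial visit".

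In the analysis sections, 7.7.4 and the synopsis repeat the reliability analysis in a remote context by intraclass correlation, with no acceptance limit. Section 7 names no analysis for the offsite data. The primary analysis (7.3 to 7.6), the Bland-Altman and vector analyses (7.7.1) and the homogeneity analyses (7.7.2) do not mention offsite or remote readings and are not split by setting.

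**The concern.** Comparing the device with itself answers whether the setting changes its reading. It does not answer whether the refraction obtained in that setting agrees with the phoropter, which is the question the trial is built on. Error common to the LFR-260 design is present in both readings and drops out of the planned comparison. A setting shift in the same direction as the in-clinic error adds to it, and the plan never scores the sum.

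At stake is the evidence for the offsite and remote uses. The trial could report close agreement between LFR-260 readings across settings and still hold no estimate of how many offsite or remote refractions satisfy its own definition of good agreement. The primary test is not affected.

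**Working it through.** **The plan's own figure.** Inputs from sections 7.4 and 7.5: performance goal 0.80, true probability 0.90, one-sided alpha 0.05, 216 eyes. The smallest r with P(X ≥ r | 216, 0.80) ≤ 0.05 is 183 (84.7%), with actual alpha 0.046. Power is P(X ≥ 183 | 216, 0.90) = 0.995, so the stated 99% reproduces, treating eyes as independent as the plan does.

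**What each comparison measures.** For one eye:

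(remote − phoropter) = (remote − initial LFR-260) + (initial LFR-260 − phoropter)

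The second right-hand term is covered by the primary and Bland-Altman analyses. The first is the comparison named in 4.9.3 and 4.9.4. The left-hand side is not analysed anywhere. Its mean is the sum of the two means, but the proportion of eyes within limits cannot be recovered from two separate summaries.

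**Illustration, sphere only.** The documents give no SD and no bias, so these are assumptions: SD 0.25 D for each paired difference, in-clinic bias 0.15 D, setting shift 0.25 D in the same direction. The proportion within 0.5 D is Φ((0.5 − b)/s) − Φ((−0.5 − b)/s).

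- In clinic against phoropter, b = 0.15: Φ(1.40) − Φ(−2.60) = 0.919 − 0.005 = 0.915.
- New setting against initial LFR-260, b = 0.25: Φ(1.00) − Φ(−3.00) = 0.841 − 0.001 = 0.840.
- New setting against phoropter, b = 0.15 + 0.25 = 0.40: Φ(0.40) − Φ(−3.60) = 0.655.

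The same calculation over a range of SD:

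| SD (D) | In clinic vs phoropter | New setting vs initial LFR-260 | New setting vs phoropter |
|---|---|---|---|
| 0.15 | 99% | 95% | 75% |
| 0.20 | 96% | 89% | 69% |
| 0.25 | 91% | 84% | 66% |
| 0.30 | 86% | 79% | 63% |
| 0.35 | 81% | 75% | 61% |

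Using one SD for all three comparisons is deliberate. Random error in the initial LFR-260 reading enters the two right-hand terms with opposite sign and drops out of their sum. If the two steps were instead independent, the SD would be 0.25 × √2 = 0.354 D and the last proportion at SD 0.25 would be 61% rather than 66%.

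**What the subsets can support.** Each setting has 21 × 2 = 42 eyes. Treating eyes as independent, an exact one-sided 95% lower bound above 0.80 needs 39/42 (bound 0.826); 38/42 gives 0.795. The chance of reaching 39/42 at a true 0.90 is 38%. Pooling both settings (84 eyes) needs 74/84 (bound 0.806), with 78% power. Correlation between the two eyes of a subject would normally weaken these figures further.

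**The case against.** The strongest reply is that little is hidden. LFR-260 bias against the phoropter is measured in every subject, and section 7.7.1 includes an evaluation of systematic bias. The setting shift is exactly what 4.9.3 and 4.9.4 compare. With SD 0.25 D and only 21 independent units, the standard error is 0.25/√21 = 0.055 D, so a 0.25 D shift is about 4.6 standard errors. This stands for mean bias, provided a paired mean difference is reported. The only statistic named is the intraclass correlation. With an assumed between-eye SD of 2 D and error SD of 0.2 D, even a 0.5 D shift leaves the absolute-agreement version at 4/(4 + 0.125 + 0.04) = 0.96. And the per-eye pass rate is missing either way.

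Other points on that side also stand. Comparison with the initial reading isolates the setting effect and is worth keeping. Offsite and remote testing are not listed among the primary or secondary endpoints. In the remote subset the patient stays in the clinic and only the examiner moves.

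A reader might go further in three ways that the documents do not support:

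- That all device bias cancels. Offsite testing uses a second unit ("An additional LFR-260 will be set up in a remote location (room separate from clinic"), so unit-specific bias does not cancel there; only bias common to the design does.
- That each step would formally pass a 0.5 D tolerance. That limit is defined only against the phoropter; none is set for one LFR-260 reading against another.
- That a large in-clinic bias would slip through. With 0.25 D at each step and SD 0.25 D, agreement with the phoropter falls from 84% in clinic to 50%. But at 84% the chance of reaching 183/216 is only 43% even if sphere were the sole component, so that scenario more often describes a trial that misses its primary goal. The 0.15 D illustration avoids this.

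**Conclusion.** The concern holds as a gap in the choice of comparator. The plan contains no estimate of offsite or remote agreement with its own gold standard, although it claims those uses and has the reference reading for the same eyes at the same visit. It does not hold as a claim that error goes wholly undetected: in-clinic bias is reported, and the setting shift could be read from the planned comparison if a mean difference were given. What is missing is the total error and the proportion of eyes meeting the three-part criterion.

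The size depends on bias and SD values that the documents do not supply. With an in-clinic bias of 0.15 D and a same-direction shift of 0.25 D, the loss in sphere agreement is 20 to 27 percentage points across SD 0.15 to 0.35 D. With no setting shift, or one in the opposite direction, that loss would not arise. This is a change that should be made, but it does not bear on the validity of the primary test.

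**What to change.** - In 4.9.3 and 4.9.4, state that sphere, cylinder and axis are recorded at the added refraction. Best corrected visual acuity is the only measurement these sections name as collected; the refraction values are implied by the comparison but not stated.
- In 4.9.3, 4.9.4 and 7.7, score each offsite and remote refraction against the same-visit phoropter reading with the three-part primary criterion.
- Report, per setting, the proportion of eyes meeting the criterion with a confidence interval that allows for two eyes per subject, and the mean difference and limits of agreement for each component.
- Keep the comparison with the initial LFR-260 reading, labelled as the setting effect.
- Label the phoropter comparison as descriptive and supplementary, not as a second test against 0.80.

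The cost is protocol and SAP wording, possibly case report form wording, and one table. No subjects, visits or refractions are added. The drawback is imprecision: 42 eyes of 21 subjects per setting will give wide intervals.

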# 4.9.5 Subject Discontinuation or Withdrawal

Subjects may withdraw their consent to participate in the clinical study at any time, for any reason. In addition, it may be necessary to terminate a subject from the clinical study due to medical safety consideration, non-compliance, or administrative concerns. If for any reason a subject is withdrawn or terminated before completing the study, the reasons for withdrawal or termination must be documented. If a subject is withdrawn or terminated due to medical safety considerations because of an adverse event, the adverse event must be followed by medical attention to satisfactory resolution and all study data related to the subject will be reported.

Subjects who withdraw or are withdrawn prior to completion of the study periods will be scheduled a termination visit. At this visit, all study procedures will be completed according to the next

scheduled visit per protocol. All pertinent data will be documented in the source documents and the CRFs including a Study Exit form

If the site is notified that a subject plans to withdraw during a study visit, the site will treat the current visit like the termination visit by completing the current visit (if able), all applicable source documents and the CRFs including the Study Exit CRF.

# 4.10 Study Duration

All subjects will be followed only for the initial visit as no follow-up assessments are expected after the initial visual acuity testing is complete.

#### 4.11 Clinical and Functional Assessments

Subjects will be clinically evaluated by the Investigator or a qualified individual noted on the Delegation of Authority (DOA) log. Clinical and functional assessments will be measured as follows:

- Patient satisfaction with LFR-260 device Quad view
- Head injury / concussion sub-group assessment (if applicable)
  - o Measure any cognitive issues or nauseous experience to refraction.

# 4.12 Prior, Concomitant, and Excluded Therapy

All concomitant medications/therapies should be collected starting at Visit 1.

# 5.0 Safety Evaluation

Adverse events are defined as any untoward medical occurrence, unintended disease or injury, or untoward clinical signs (including abnormal laboratory findings) in subjects, users, or other persons, whether or not related to the investigational medical device. See section 8.0 for anticipated risks during the trial.

All adverse events will be collected and recorded, regardless of whether or not they are believed to be related to the device or anticipated. This includes the following:

- Adverse Device Effect (ADE) adverse event related to the use of an investigational medical device.
- Serious Adverse Events (SAE) an adverse event that led to death; led to serious deterioration in the health of the subject, that either resulted in: a life-threatening illness or injury; a permanent impairment of a body structure or a body function; in-patient or prolonged hospitalization; medical or surgical intervention to prevent life-threatening

illness or injury or permanent impairment to a body structure or a body function; led to fetal distress, fetal death or congenital abnormality/birth defect.

- Unanticipated Adverse Device Effect (UADE) any serious adverse effect on health or safety or any life-threatening problem or death caused by, or associated with, a device, if that effect, problem, or death was not previously identified in nature, severity, or degree of incidence in the investigational plan or application (including a supplementary plan or application), or any other unanticipated serious problem associated with a device that relates to the rights, safety, or welfare of subjects.
- Device deficiency inadequacy of a medical device with respect to its identity, quality, durability, reliability, safety or performance.

#### 5.1 Serious Adverse Event Parameters

At any point during the clinical investigation, study termination or unblinding may be considered based on the frequency or severity of serious adverse device effects or serious adverse events. If this occurs, subjects will be notified of the study termination and follow-up requirements, as applicable. Every effort will be made to collect data regarding the subject disposition following such an event.

# 5.2 AE / SAE Recording and Reporting

Any and all adverse events will be recorded on the Adverse Event Case Report Form. Investigators are required by federal regulations, to report all adverse events that occur during the course of a study to Evolution Optiks or their designee. All adverse events reported on the Case Report Form will be source data verified against the subject record. The site is also responsible for reporting adverse events to the governing IRB in accordance with the requirements of that IRB.

Serious Adverse Events are to be reported to Evolution Optiks or their designee within 24 hours of the investigator's awareness of their occurrence. The Investigator is also required to report any UADEs to Evolution Optiks or their designee within 24 hours. The Investigator is also responsible for reporting these events to the governing IRB in accordance with the requirements of that IRB.

The names and telephone numbers of the contact persons from Evolution Optiks or its designated representative are given in the table below:

SERIOUS ADVERSE EVENT SPONSOR CONTACT INFORMATION					
Name/Title	Email	Office Telephone Number	Mobile Telephone Number		
[name], MS Project Manager	[contact]	$\times\!\!\times\!\!\times\!\!\times$	$\times\!\!\times\!\!\times\!\!\times$		
		$\times\!\!\times\!\!\times\!\!\times$	$\times\!\!\times\!\!\times\!\!\times$		
		$\times\!\!\times\!\!\times\!\!\times$	$\times$		

# 6.0 Clinical Supplies

# 6.1 Receiving, Storage, Dispensing and Return of Investigational Product

# 6.1.1 Receipt and Accountability

It is the responsibility of the Investigator to ensure that all product received at the site are inventoried and accounted for throughout the study and recorded in the Product Accountability (inventory) log kept in the site study documents.

# 6.1.2 Storage and Return or Destruction of Investigational Product

The Investigator will store the investigational product and dispose of remnants per the Sponsor's instructions. Unopened product will be returned to the Sponsor. Product Accountability will be recorded in the source documentation and in the Product Accountability log for monitor review and reconciliation.

# 6.1.3 Dispensing of Investigational Device

The Investigator will not supply study material to any person except designated staff participating in this study. Study material will only be dispensed from the designated investigational site to eligible study subjects.

# 7.0 Statistical Analysis

# 7.1 Study Design and Randomization

The LFR-260-101 study is a multi-center, open-label, 2x2 cross-over design with the aim of investigating the effectiveness of the LFR-260 phoropter device compared to the traditional phoropter.

# 7.2 Analysis Sets

# 7.2.1 Intent-to-Treat (ITT)

All randomized patients will be included in the intent-to-treat (ITT) analysis set according to the group to which they were randomized.

# 7.2.2 Full Analysis Set (FAS)

The Full Analysis Set (FAS) analysis set will be defined similarly to the ITT analysis set except that patients will be analyzed according to the order of devices actually administered. Primary safety analyses will be conducted in the FAS analysis set. If all ITT patients receive their intended device order, the FAS and ITT analysis sets will coincide and will be referred to as the ITT analysis set.

#### 7.2.3 Per Protocol

Primary effectiveness analyses may be repeated in a Per Protocol (PP) analysis set. The PP analysis set will exclude from the ITT analysis set patients that had clinically significant violations of inclusion or exclusion criteria or post randomization protocol violations that may reasonably be predicted to impact on effectiveness endpoints and those that have missing data.

# 7.3 Primary Effectiveness Endpoint

The primary effectiveness endpoint is to demonstrate that the LFR-260 is within 0.5D (+/-) in measuring sphere and cylinder results and within 10 degrees for axis results among subjects with low astigmatism and within 5 degrees among subjects with moderate to high astigmatism from the traditional phoropter in a very large proportion of subjects.

# 7.4 Primary Effectiveness Hypothesis

The primary hypothesis for this study is that the probability of simultaneously achieving good clinical agreement for sphere, cylinder, and axis exceeds a performance goal for measurements made by the LFR-260 compared to those obtained using the control device, *traditional phoropter*.

Symbolically, the null and alternative effectiveness hypotheses are: :

Ho:  $\pi \le PG$ Ha:  $\pi > PG$ 

Where  $\pi$  is the true probability that the LFR 260 is within 0.5D (+/-) in measuring sphere and cylinder results and within 10 degrees for axis results among subjects with low astigmatism and within 5 degrees among subjects with moderate to high astigmatism from the traditional phoropter.

For this study, PG is set to 0.80.

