#### 3.4 Inclusion criteria

Participants must fulfill all of the following criteria in order to be eligible for the study:

- 1. The participant or legal guardian is willing and able to understand, sign and date the Ethics committee approved study specific Informed Consent Form.
- 2. The participant is a male or female between the ages of 12 and 65 (inclusive).
- 3. The participant has a history of the following:
  - O No more than mild to moderate far-sightedness or near-sightedness (i.e. Spherical equivalent refraction (SER) between +10 to -15).
  - o an astigmatism of 2.5D or less.
  - o an anisometropia of 1.5D or less.
- 4. The participant is free of ocular and systemic abnormalities that might affect visual functions.

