# 7.5 Sample Size Determination

If the true  $\pi$  is equal to 0.90, then, a 1-sided exact binomial test at alpha=0.05 with 216 eyes (108 subjects) has 99% power.

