# 7.6 Testing of Primary Effectiveness Hypothesis

The lower bound (LB) of a 1-sided exact binomial confidence interval will be determined and compared to 0.80. If LB exceeds 0.80, the device will have met the a priori defined performance goal.

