# 7.7 Other Planned Analyses

#### 7.7.1 Bland-Altman Agreement Analysis

Supporting analyses will evaluate the distribution of paired differences between LFR-260 and reference for the three dimensions (sphere, cylinder, and axis) using Bland-Altman agreement analysis. This will include determination of the standard deviation of paired differences, the 95% limits of agreement, and an evaluation of systematic bias. The Bland-Altman plot of paired differences versus the mean of measurements will be provided. The relationship between bias and the mean of measurements will characterized. The same analysis will be applied to the vector difference between LFR-260 measurements and the gold standard in terms of sphere and cylinder measurements. The vector differences is square root of (X1-Y1) + (X2-Y2) where the X1 and X2 are measurements of sphere and cylinder using the investigational devices and Y1 and Y2 are the same measurements using the gold standard.

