# 7.7.4 Reliability and Repeatability Analysis

Reliability of LFR-260 will be conducted in a subset of subjects for which measurements will be obtained twice in an office context. This analysis will be repeated in a remote context. Reliability will be evaluated using intraclass correlations for each of the continuous measurements, sphere, cylinder, and axis and for the vector measurement of sphere and cylinder.

For a subset of 33 subjects (66 eyes), the LFR-260 device will be measured again approximately 60 minutes after the initial assessment in order to measure the repeatability/accuracy of the device.

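### Axis agreement is scored in degrees with only a coarse two-tier split by astigmatism, so optically small differences at low cylinder count as failures, and no planned analysis combines cylinder and axis to show this

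*Combined protocol and SAP*

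**What the plan says.** The primary hypothesis (section 7.4) is that "the probability of simultaneously achieving good clinical agreement for sphere, cylinder, and axis exceeds a performance goal". Sphere and cylinder must each lie within 0.5 D of the phoropter, and axis must lie "within 10 degrees for axis results among subjects with low astigmatism and within 5 degrees among subjects with moderate to high astigmatism". The goal is fixed: "For this study, PG is set to 0.80". Section 7.6 gives the decision rule: "If LB exceeds 0.80, the device will have met the a priori defined performance goal". Section 7.5 states that, for a true probability of 0.90, "a 1-sided exact binomial test at alpha=0.05 with 216 eyes (108 subjects) has 99% power".

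No section says at what cylinder power low astigmatism ends. Sections 2.1 and 2.3 give 10 degrees without tiers, and the synopsis attaches both limits to low astigmatism. Eligibility (section 3.4) sets only an upper limit, "an astigmatism of 2.5D or less", so eyes with 0.25 or 0.50 D of cylinder are enrolled.

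Supporting analyses treat axis as a variable on its own. Section 7.7.1 applies Bland-Altman to sphere, cylinder and axis separately, then adds: "The same analysis will be applied to the vector difference between LFR-260 measurements and the gold standard in terms of sphere and cylinder measurements". Axis does not enter that vector. Section 7.7.2 compares sites and demographic subgroups for each component and for the same vector. Section 7.7.4 plans "intraclass correlations for each of the continuous measurements, sphere, cylinder, and axis", again with the sphere-cylinder vector. None of these is broken down by cylinder power.

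**The concern.** The optical effect of an axis difference grows with cylinder power. A limit in degrees that is constant within a tier is therefore tightest, in dioptres, for the eyes with the least cylinder in that tier. In those eyes small measurement noise produces large swings in axis, so an unbiased device can collect failures that have little optical meaning. Because sphere, cylinder and axis must all pass, each such failure counts fully against the 0.80 goal.

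The supporting analyses would normally show whether that had happened. They cannot do so here. Axis differences in degrees mix noise at 0.25 D with real error at 2.50 D, and the planned vector does not use axis. If the goal is narrowly missed or met, the report could not say how large the astigmatic disagreement was in dioptres. A dioptric analysis added after the results are known would look like a rescue.

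**Working it through.** **Inputs from the documents.** 216 eyes, goal 0.80, planning value 0.90, one-sided alpha 0.05 (7.4 to 7.6); axis limits of 10 and 5 degrees, cylinder limit 0.5 D (7.4); cylinder up to 2.5 D with no minimum (3.4).

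**Step 1. The plan's own figure.** The smallest r with P(X >= r | 216, 0.80) <= 0.05 is 183 (84.7%), with exact alpha 0.0461. P(X >= 183 | 216, 0.90) = 0.9946, so the stated 99% reproduces. The rule allows 216 - 183 = 33 failing eyes. At 0.90, 216 x 0.10 = 21.6 failures are expected, so about 34 - 21.6 = 12.4 extra failures miss the goal.

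**Step 2. Axis limits in dioptres.** If both devices give the same cylinder C and the axes differ by t, the astigmatic vector difference on the full-cylinder scale is 2 x C x sin(t). It equals 0.50 D at t = arcsin(0.25/C).

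| Cylinder | Size of 10 degrees | Size of 5 degrees | Angle giving 0.50 D |
|---|---|---|---|
| 0.25 D | 0.087 D | 0.044 D | 90 degrees |
| 0.50 D | 0.174 D | 0.087 D | 30 degrees |
| 0.75 D | 0.260 D | 0.131 D | 19.5 degrees |
| 1.00 D | 0.347 D | 0.174 D | 14.5 degrees |
| 1.50 D | 0.521 D | 0.261 D | 9.6 degrees |
| 2.50 D | 0.868 D | 0.436 D | 5.7 degrees |

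Comparing 5 degrees at 2.50 D with 10 degrees at low cylinder: 0.436/0.174 = 2.5 at 0.50 D, and 0.436/0.087 = 5.0 at 0.25 D. An 11-degree difference at 0.25 D (0.095 D) fails, while a 5-degree difference at 2.50 D (0.436 D) passes. The same happens at the bottom of the upper tier: if 1.00 D falls there, its limit is 0.174 D, the same as for 0.50 D at 10 degrees.

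**Step 3. The planned vector.** Take -2.00/-2.00 at axis 180 and at axis 90. Sphere and cylinder differences are both 0, so the vector in 7.7.1 is 0. The astigmatic difference is 2 x 2.00 x sin(90) = 4.0 D on the full-cylinder scale.

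**Step 4. Possible effect on the result (assumptions, not in the documents).**

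*Simple model.* A share f of eyes has very low cylinder, and a share q of those that would otherwise agree fails on axis alone: pi = 0.90 x (1 - f x q).

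| f | q | pi | P(at least 183 of 216) |
|---|---|---|---|
| 0.2 | 0.1 | 0.882 | 95.0% |
| 0.2 | 0.2 | 0.864 | 79.6% |
| 0.3 | 0.2 | 0.846 | 52.6% |
| 0.4 | 0.2 | 0.828 | 25.9% |
| 0.4 | 0.3 | 0.792 | 2.5% |

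For scale, normal axis differences with SD 7.5 or 10 degrees in those eyes would give q = 0.18 or 0.32.

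*Noise model.* No bias, sphere always passes, and the two readings differ by Gaussian error with SD s in each of C cos2a and C sin2a. Cylinders run from 0.25 to 2.00 D with 45% of eyes at 0.25 to 0.50 D, and the low tier ends at 0.75 or 1.00 D (hence the ranges).

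| s | Axis within 10 degrees at 0.25 D | at 0.50 D | pi | P(at least 183) | Eyes within 0.50 D astigmatic vector difference |
|---|---|---|---|---|---|
| 0.10 D | 61% | 91% | 0.88-0.90 | 96-99% | 100% |
| 0.15 D | 44% | 75% | 0.76-0.79 | 0.1-2% | 99.6% |
| 0.20 D | 34% | 61% | 0.64-0.68 | about 0 | 95.6% |

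The last column is 1 - exp(-0.50^2/(2s^2)). At s = 0.05 D pi is 0.98 and there is no problem. At s = 0.15 D, three assumed cylinder mixes give pi from 0.71 to 0.85. A bound needing no detail on the other 55% of eyes: if they all passed at s = 0.15 D, pi would be 0.55 + 0.45 x 0.75 = 0.89 with the 45% all at 0.50 D, and 0.55 + 0.45 x 0.44 = 0.75 with them all at 0.25 D. Over s of 0.10 to 0.20 D in the 45% mix, 64 to 97% of failures come from eyes with at most 0.50 D of cylinder.

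**The case against.** Several points against this are sound.

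- A reader might infer that the criterion ignores cylinder power. It does not: the 10/5-degree tiers are a coarse weighting by astigmatism. They narrow the imbalance without removing it.
- A reader might infer that large axis errors in high-cylinder eyes go unseen. The primary endpoint catches them: 90 degrees at 2.00 D, or 20 degrees at 2.50 D, fails under either tier, and axis has its own Bland-Altman analysis. What is missing is their size in dioptres.
- A reader might infer that the 99% power is wrong or that the device will fail. The power is correct for its planning value of 0.90. The documents give no axis variability, cylinder distribution or tier boundary, and nothing in them favours one assumed SD over another.
- The rule is conservative. It makes success harder and does not raise the chance of false success.
- A reader might infer that the degree rule should be replaced. It was set in advance and is a legitimate choice. A 0.50 D vector limit would accept any axis at 0.25 D, 30 degrees at 0.50 D, 14.5 at 1.00 D and 9.6 at 1.50 D when cylinders are equal, which is a debatable loosening.

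All of this argues for leaving the primary rule alone. None of it supplies an analysis that combines cylinder and axis.

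**Conclusion.** The point holds in a limited form. Geometry alone establishes that the axis limit is 2.5 to 5 times stricter in dioptres at 0.50 and 0.25 D of cylinder than 5 degrees is at 2.50 D. The text alone establishes that no planned analysis joins cylinder and axis. Neither conclusion needs an assumption about variability.

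The consequence for the primary result is conditional. About 12 axis-only failures beyond those expected at 0.90 would miss the goal. Under the assumed component SDs of 0.10 to 0.20 D, the outcome ranges from little effect to near-certain failure to reach 183 of 216, even though at least 95.6% of eyes would be within 0.50 D in astigmatic vector difference. The documents do not show where in that range the trial lies. This should be corrected in the supporting and sensitivity analyses; it is not a ground for changing the primary endpoint. The power figures treat eyes as independent, as the plan does; that is a separate matter.

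**What to change.** Keep the degree rule as primary, and make three changes before database lock.

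1. In 7.7.1, 7.7.2 and 7.7.4, and in the matching synopsis text, replace the sphere-cylinder vector with a power-vector analysis: M = S + C/2, J0 = -(C/2) cos2a, J45 = -(C/2) sin2a. Use J0 and J45 in place of raw axis degrees for Bland-Altman, homogeneity and intraclass correlations.
2. Pre-specify a sensitivity analysis of the primary endpoint that keeps the sphere criterion and scores cylinder and axis together: sqrt[(C1 cos2a1 - C2 cos2a2)^2 + (C1 sin2a1 - C2 sin2a2)^2] <= 0.50 D. State that this is the full-cylinder scale, twice the J0/J45 distance.
3. Report primary-endpoint failures by component (sphere, cylinder, axis) and by cylinder band.

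The cost is a little more analysis work and some wording. Section 4.3 already records sphere, cylinder and axis separately for both devices, so no new data are needed.

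The downside should be stated in the plan. With equal cylinders, the sensitivity rule is more lenient on axis than the degree rule, markedly so up to about 1.50 D and slightly at 2.50 D (5.7 against 5 degrees). It is stricter when power and axis differences combine: 2.50 against 2.00 D with axes 5 degrees apart gives sqrt(6.25 + 4.00 - 10 x cos10) = 0.63 D, which fails it but meets the 5-degree and 0.5 D limits. It therefore supports the primary result and does not replace it.
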